3.1.4.1 Adverse events variables

Occurrence of adverse events (including serious adverse events [SAEs], and adverse events of special interest [AESIs]) are recorded from the time of signed informed consent until the end of study.

All adverse events will be coded to a "Lowest Level Term (LLT)", "Preferred Term (PT)", "High Level Term (HLT)", "High Level Group Term (HLGT)", and associated primary "System Organ Class (SOC)" using the version of MedDRA currently in effect at Sanofi at the time of the database lock.

Adverse event observation periods

• Pre-treatment adverse events are adverse events that developed or worsened or became serious during the pre-treatment period;

- Treatment-emergent adverse events are adverse events that developed or worsened or became serious during the treatment-emergent adverse event period;
- Post-treatment adverse events are adverse events that developed or worsened or became serious during the post-treatment period.

Adverse events of special interest

Adverse events of special interest (AESIs) are adverse events (serious or non-serious) that need to be monitored, documented, and managed in a pre-specified manner described in the protocol. In this study, AESI are the following (their complete descriptions are provided in the protocol):

- General allergic events, selected using SMQ "hypersensitivity" (broad and narrow) excluding the following preferred terms linked to local injection site reactions ("infusion site dermatitis", "infusion site hypersensitivity", "infusion site rash", "infusion site urticaria", "injection site dermatitis", "injection site hypersensitivity", "injection site rash", "injection site urticaria", and "injection site vasculitis")
- Local injection site reactions, selected using e-CRF specific tick box on the adverse event page
- ALT ≥3 ULN (if baseline ALT <ULN) or ALT ≥2 times the baseline value (if baseline ALT ≥ULN), selected using laboratory data
- Hemolytic anemia, selected using e-CRF specific tick box on the adverse event page and confirmed final diagnosis provided in the adverse event complementary form
- Neurologic events selected using a CMQ, based on SMQs "demyelination" (broad and narrow), "peripheral neuropathy" (broad and narrow), and "Guillain-Barre syndrome" (broad and narrow) excluding the following preferred terms "acute respiratory distress syndrome", "asthenia", "respiratory arrest" and "respiratory failure" and including selected PTs from SMQ "optic nerve disorders" (see Appendix B Table 13 for the list of terms)
- Neurocognitive events:
 - Selected using a CMQ, based on the following 5 HLGTs: "deliria (including confusion)", "cognitive and attention disorders and disturbances", "dementia and amnestic conditions", "disturbances in thinking and perception", and "mental impairment disorders"
 - A second grouping of terms for neurocognitive events was defined based on Regulatory Agency request (see Appendix B Table 14 for the list of terms)
- Overdose of IMP (symptomatic or asymptomatic), selected using appropriate MedDRA codes and the tick box "Overdose with IMP" in the adverse event complementary e-CRF form
- Pregnancy (including partner of a randomized male subject) selected using appropriate MedDRA codes

In addition the additional grouping of events will be provided:

- Hepatic disorder events using SMQ "Hepatic disorder"
- Diabetes mellitus or diabetic complications using HLGT "diabetes complications" (including PTs pertaining to the secondary SOC included in the HLGT), HLT "diabetes mellitus", and HLT "carbohydrate tolerance analyses (incl diabetes)" excluding PTs "blood glucose decreased" and "Glycosylated haemoglobin decreased" and including the PTs "hyperglycaemia", "Hyperglycaemic unconsciousness" and "Hyperglycaemic seizure" from the HLT "Hyperglyceamic conditions NEC"
- New onset of diabetes (in the subgroup of patients not having diabetes at baseline) (see definition in Section 3.4.5.3)
- Cataract using HLT "Cataract conditions"

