### **9.2.1 Adverse event**

All adverse events diagnosed by the Investigator, irrespective of the result of the adjudication for cardiovascular events, will be reported and described.

All AEs will be coded to a “Lowest Level Term (LLT)”, “Preferred Term (PT)”, “High Level term (HLT)”, “High Level Group Term (HLGT)” and associated primary “System Organ Class (SOC)” using the version of MedDRA (Medical Dictionary for Regulatory Activities) currently in effect at Sanofi at the time of the considered database lock.

AEs of special interest include, but are not limited to, the following:

- Allergic events (using special eCRF pages, see [Section 10.6.2](#))
- Local injection site reactions (using special eCRF pages, see [Section 10.6.1](#))
- Hemolytic anemia (using special eCRF pages, see [Section 10.4.7.1](#))

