#### 10.4.6 Guidelines for reporting adverse events of special interest

##### 10.4.6.1 Reporting of adverse events of special interest with immediate notification

For these AEs, the Sponsor will be informed immediately (ie within 24 hours), as per SAEs notification described in [Section 10.4.5](#), even if not fulfilling a seriousness criterion, using the corresponding screens in the eCRF.

- ALT  $\geq 3$  ULN (if baseline ALT < ULN) Or ALT  $\geq 2$  times the baseline value (if baseline ALT  $\geq$  ULN) (Please refer to related flowchart in [Appendix C](#)).
- Allergic events
  - Allergic drug reactions and/or local injection site reactions deemed to be allergic (or have an allergic component) that require consultation with another physician for further evaluation of hypersensitivity/allergy, as per the investigator's medical judgment or as per [Section 10.6.2](#), should be reported as an AESI with immediate notification.
  - All allergic events, and all injection site reactions having an allergic component or deemed to be allergic, require completion of the specific eCRF screen (see [Section 10.6.2](#)), regardless of requirements for immediate reporting.

- Hemolytic anemia (see [Section 10.4.7.1](#) and [Appendix D](#))
  - If there is a decrease in hemoglobin and reflexive testing as per [Appendix D](#) suggesting hemolysis, then report this as an AESI with immediate notification. Special eCRF screen will need to be completed
- Pregnancy
  - *Pregnancy occurring in a female patient enrolled in the study* will be recorded as a pre-specified AE with immediate notification in all cases, and IMP should be discontinued in all cases. It will be qualified as an SAE only if it fulfills the SAE criteria. The follow-up of the pregnancy will be mandatory until the outcome of the pregnancy has been determined.
  - *Pregnancy occurring in the female partner of a male patient included in the clinical trial*: if permitted by the female partner and by local regulatory policies, it will be recorded as a pre-specified AE with immediate notification (SAE if it fulfills the SAE criteria), and pregnancy should be followed-up until the outcome has been determined.
- Symptomatic Overdose with IMP

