#### **10.4.6.2 Reporting of adverse events of special interest without immediate notification**

See [Appendix E](#).

For these AEs, the Sponsor does not have to be informed immediately, unless meeting seriousness criterion.

- Asymptomatic overdose with IMP
  - An overdose (accidental or intentional) is an event suspected by the Investigator or spontaneously notified by the patient (not based on systematic injection counts) and defined as at least twice of the intended dose within the intended therapeutic interval (ie, 2 or more injections from the double-blind treatment kit are administered in <7 calendar days); to be reported using the corresponding screens in the eCRF using

the Term “asymptomatic OVERDOSE (accidental [or intentional])” The patient should be monitored for any AEs and treated, as needed

- Local injection site reactions (see [Section 10.6.1](#))
  - Local injection site reactions related to IMP that are considered as non-allergic events should be further characterized by evaluating the related symptoms that comprise an injection site reaction such as but not limited to redness, pain, etc (See [Appendix F](#)). Special eCRF screens will need to be completed. If such an AE was to occur, then do not report the individual components of the reaction but rather the term “local injection site reaction”, the individual components being described in the specific eCRF screen
- Allergic events not referred for consultation with another physician (see [Section 10.4.6.1](#))
  - All allergic events will need to have allergy specific eCRF screens completed (see [Section 10.6.2](#)), regardless of requirements for immediate reporting.
- Neurologic and Neurocognitive events
  - AEs related to neurologic or neurocognitive abnormalities with the exception of those requiring additional examinations/procedures and/or referral to a specialist (as mentioned in [Section 10.4.6.1](#)) should be reported in accordance with [Appendix E](#).

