### 10.6.2 Allergic adverse events (See [Section 10.4.6.1](#) and [Section 10.4.6.2](#))

Specific eCRF screens are to be filled in to assess allergic reactions or allergic-like reactions that may occur during the clinical studies conducted with alirocumab.

Sometimes transient injection site reactions, irritant in nature, may occur, requiring no intervention and being of dubious significance. These reactions would not be considered to be allergic reactions.

Adverse events that may constitute an allergic reaction (eg, generalized itch, nasal itch, swelling at injection site, flushing, hives, swelling at lips, eyes, face, tongue, hands, feet, lump in throat, difficulty to swallow, hoarseness, change in pitch of voice, incapacity to speak, wheezing, chest tightness, stridor, etc) should be considered to be reported on the General Allergic Reaction and/or Local Injection Site Reaction Complementary Form.

Adverse events that are obviously not of allergic origin (eg, local injection site reactions related to IMP and with no allergic component) should only be recorded on the Local Injection Site

Reaction Complementary Form. However, injection site reactions which progress/expand/worsen/etc should be evaluated as recommended in [Section 10.6.2.1](#) and General Allergic Reaction Complementary form should be completed.

The IMP should be immediately interrupted (temporarily discontinued) if there is a suspicion of an allergic event related to IMP. See [Section 10.3.1](#) for further information on treatment interruption and [Section 10.3.2](#) for criteria for permanent treatment discontinuation.

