#### **11.4.3.1 Adverse events**

Adverse event incidence tables will present by system organ class (SOC) (sorted by internationally agreed order), high-level group term (HLGT), high level term (HLT) and preferred term (PT) sorted in alphabetical order for each treatment group, the number (n) and percentage (%) of patients experiencing an AE. Multiple occurrences of the same event in the same patient will be counted only once in the tables within a treatment phase. The denominator for computation of percentages is the safety population within each treatment group.

Adverse event incidence table will be provided by treatment group for all types of TEAEs: all TEAEs, all treatment emergent AESI (defined with a PT or a prespecified grouping), all treatment emergent SAEs and all TEAEs leading to permanent treatment discontinuation. If any clinically significant signal is detected and need further characterization or for adverse event of clinical interest (eg, injection site reaction, allergic reaction), exploration of time to onset will be performed for these selected TEAEs as described below to account for the differential exposure time in all patients.

Local injection site reaction could be further described in terms of time pattern (time to first occurrence, duration, recurrence) and intensity.

Selected TEAEs will be also analyzed using time-to-event approach (Kaplan-Meier methodology). Time from the first dose of double-blind IMP injection to the first occurrence of the event will be calculated (only the first event will be counted). Patients without any event will be censored at the end of the TEAE period. Incidence rates at 6 months and by year of exposure will be presented and Kaplan-Meier curves will be provided.

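### The SAP's general allergic events grouping does not implement the protocol's allergic AESI: nine infusion- or injection-site terms are excluded and the allergy form is not used

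*SAP*

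**What the plan says.** **Protocol.** Section 9.2.1 lists allergic events as an AESI with dedicated eCRF pages. Under the allergic heading, section 10.4.6.1 asks for immediate notification of "Allergic drug reactions and/or local injection site reactions deemed to be allergic (or have an allergic component) that require consultation with another physician". It then sets the recording rule: "All allergic events, and all injection site reactions having an allergic component or deemed to be allergic, require completion of the specific eCRF screen", whether or not immediate notification applies. Section 10.4.6.2 keeps allergic events not referred to another physician as an AESI without immediate notification. It describes the separate local-reaction AESI in these terms: "Local injection site reactions related to IMP that are considered as non-allergic events should be further characterized". Under section 10.6.2, possible allergic reactions "should be considered to be reported on the General Allergic Reaction and/or Local Injection Site Reaction Complementary Form".

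**SAP.** Section 3.1.4.1 refers the reader to the protocol for the full AESI descriptions and then gives the selection rules. The allergic rule is "General allergic events, selected using SMQ 'hypersensitivity' (broad and narrow) excluding the following preferred terms linked to local injection site reactions". Four infusion-site and five injection-site terms follow. Local injection site reactions are a separate AESI, selected by a tick box on the adverse event page. For hemolytic anemia and overdose the SAP draws on a complementary eCRF form; for allergic events it does not.

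**The concern.** The protocol divides injection-site reactions by the investigator's judgment: allergic ones go with the allergic events, the others form the local-reaction AESI. The SAP divides them by coded term and tick box. The two divisions need not agree, so the grouping reported as allergic is not the AESI that the protocol describes.

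Protocol section 4 names local injection site reactions and rare hypersensitivity reactions among the identified or potential risks of the drug. Under SAP 3.4.5.1 each Tier 1 grouping gets an incidence with confidence interval, a rate per 100 patient-years, a hazard ratio and Kaplan-Meier curves. If some events that the protocol calls allergic are outside that grouping, no planned table gives these statistics for the allergic AESI as the protocol defines it.

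**Working it through.** No arithmetic applies: the point concerns a definition, and the documents give no rate for allergic injection-site reactions. The check is to follow such a reaction through both documents.

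1. **Is it an allergic AESI under the protocol?** Yes. Consultation with another physician decides only how fast it is notified: section 10.4.6.1 takes the referred events and section 10.4.6.2 the rest. The allergy screen is required in both cases.
2. **What does the SAP exclude?** Dermatitis, hypersensitivity, rash and urticaria at the infusion site (4), and the same four plus vasculitis at the injection site (5): 4 + 5 = 9 terms. The investigator's judgment plays no part.
3. **Where does the reaction land?**

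| Injection-site reaction judged allergic | Protocol | SAP grouping |
|---|---|---|
| Coded to one of the nine terms, local box ticked | Allergic AESI | Local-reaction AESI only |
| Coded to one of the nine terms, local box not ticked | Allergic AESI | Neither; appears only in the general TEAE tables |
| Coded to another term inside the SMQ | Allergic AESI | Allergic grouping, and the local one if ticked |
| Coded to a term outside the SMQ | Allergic AESI | Local-reaction AESI if ticked, otherwise neither |

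4. **Can the box be left unticked?** The protocol leaves it open. Its local-reaction AESI is worded for non-allergic reactions, and section 10.6.2 offers the General Allergic Reaction form and/or the local form for possible allergic reactions. Only reactions that are plainly not allergic are confined to the local form. The eCRF and protocol Appendices E and F are not in the text available, so actual practice cannot be checked.
5. **Are the excluded terms likely to be allergic?** Section 10.4.6.2 tells sites to report a non-allergic reaction under the single term for a local reaction and not by its components. If sites comply, a specific term such as injection site urticaria would tend to come from reactions that were not handled as plainly non-allergic. This is an inference from the reporting rule, not a finding.
6. **Does the mismatch also run the other way?** It can. The broad SMQ may take in events that no investigator called allergic, and these are in the SAP grouping without being allergic AESIs under the protocol.

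**The case against.** The strongest reply is that sections 10.4.6.1 and 10.4.6.2 are reporting rules for sites, while the protocol's own analysis section, 11.4.3.1, provides for "all treatment emergent AESI (defined with a PT or a prespecified grouping". A coded, reproducible grouping is therefore allowed. That stands as far as it goes. But permission to use a grouping does not make this one match the AESI that it is meant to represent, and the SAP itself sends the reader to the protocol for what the AESI is.

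The second reply also has force: the nine terms are not discarded. When the local box is ticked they are counted in a Tier 1 AESI with its own hazard ratio, Kaplan-Meier curves and breakdown by preferred term, and every TEAE is tabulated by preferred term in any case. But the local-reaction summaries do not separate allergic from other reactions, and the general tables do not carry the investigator's allergic judgment.

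Several stronger readings are tempting, and the documents do not support them:

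- *All injection-site hypersensitivity terms are removed, so allergic site reactions are never counted as allergic.* Nine named terms are removed. The SMQ content is not given, and a reaction coded to another term within it stays in.
- *Allergic risk is under-reported, or the hazard ratio is pulled towards 1.* Placebo patients are injected too, and protocol section 4 says that local reactions were reported in both groups. With the broad SMQ adding events, the net direction is unknown.
- *A patient count can be given.* If 2% to 6% of 9,300 alirocumab patients had a site reaction and 5% to 20% of these were judged allergic, the count would run from 9,300 × 0.02 × 0.05 = 9.3 to 9,300 × 0.06 × 0.20 = 111.6. Both shares are assumed. Reading this as the number omitted also supposes that every such reaction is coded to one of the nine terms and that the patient has no other allergic event.

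**Conclusion.** The mismatch holds. As written, the SAP's allergic grouping leaves out injection-site reactions judged allergic if they are coded to one of nine terms, and some of these can fall in neither the allergic nor the local-reaction grouping. Whether any did depends on coding and tick-box practice that the documents do not show. The size and direction of any effect on the allergic incidence or hazard ratio cannot be determined.

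This is a matter of definition and traceability in a safety analysis. It does not touch the primary endpoint, type I error or power. It is worth correcting because it concerns a named risk, the protocol requires an allergy form that the SAP text does not analyse, and the remedy is small.

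**What to change.** In SAP 3.1.4.1, keep the current general allergic events grouping and add one supplementary Tier 1 grouping: the current SMQ selection plus any injection-site reaction recorded as allergic, or as having an allergic component, on the General Allergic Reaction form. Report it with the same Tier 1 statistics, and list any such reaction that falls in neither the current allergic grouping nor the local-reaction AESI. The SAP already sets a precedent by giving neurocognitive events a second grouping.

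The cost is some SAP wording and one more set of tables from data that the protocol already collects. Some patients will appear in both the allergic and the local-reaction rows, which a footnote should say. One limit remains: an allergic reaction entered on the local form alone would still be missed, so the SAP should state whether that form also records the allergic judgment.

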### **9.2.2 Safety laboratory**

The clinical laboratory data consist of hematology (red blood cell count, reticulocyte count, hemoglobin, hematocrit, platelets, white blood cell count [WBC] with differential blood count), standard chemistry (glucose, sodium, potassium, chloride, bicarbonate, calcium, phosphorous, urea nitrogen, creatinine, uric acid, LDH, total protein, albumin,  $\gamma$  Glutamyl Transferase [ $\gamma$ GT]), Hepatitis C antibody, liver panel (ALT, AST, alkaline phosphatase [ALP], and total bilirubin), and CPK.

Some additional safety laboratory parameters may be reflexively measured, based on actual data (please refer to [Section 10.4.7](#)).

Clinical laboratory values will be analyzed after conversion into standard international units. Standard international units will be used in all listings and tables.

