#### 10.4.7 Guidelines for management of specific laboratory abnormalities

Laboratory abnormalities with pre-specified monitoring should be monitored, documented, and managed according to the related flowchart in protocol [Appendix C](#) and [Appendix D](#)

- Neutropenia
- Thrombocytopenia
- Increase in ALT
- Acute renal insufficiency
- Decrease in hemoglobin (defined as  $\geq 1.5$  g/dL decrease from pre-randomization baseline value)
- Increase in CPK (other than cardiac-related) and suspicion of rhabdomyolysis.

Investigators are strongly encouraged to follow these algorithms in [Appendix C](#) and [Appendix D](#), especially in situations where the abnormality persists or when there is no clear explanation for the observed abnormality.

However there may be situations where these algorithms are not entirely applicable, therefore Investigator may use his/her best judgment. Also, in some situations, the Sponsor may wish to discuss with the Investigator. Examples where these algorithms may not be applicable include (but are not limited to) the following situations:

- patients with known stable low or borderline neutrophil or platelet count or impaired renal function at baseline; Investigator should attempt to have a diagnosis for the observed finding and should use his/her best judgment whether or not to enroll these patients, and if

patient is enrolled, on how to best monitor these baseline abnormalities throughout the study

- patients with ALT increase or elevated CK for which the abnormality resolves following statin dose reduction or statin discontinuation
- patients with elevated CK caused by a myocardial infarction

In addition, discontinuation caused by a laboratory abnormality can be either permanent or temporary, depending on the particular case. There is no requirement for permanent treatment discontinuation in every case of the general guidance for the follow up of selected laboratory abnormalities mentioned in [Appendix C](#).

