#### **10.4.7.1 Hemoglobin decrease**

See [Appendix D](#).

At the first post-randomization study visit with occurrence of a hemoglobin (Hb) measurement decrease by  $\geq 1.5$  g/dL as compared to the randomization visit hemoglobin measurement, then the Central Lab will reflexively measure haptoglobin using specimens already obtained at the same time point for which the hemoglobin decrease was detected. The Central Lab will then provide the results of the reticulocyte count, haptoglobin, LDH and indirect bilirubin (reflexively measured only if the total bilirubin  $>$  ULN) to the Investigator.

***NOTE:** At selected sites with a longer transit time to Central Lab where reticulocyte count cannot be measured by Central Lab, a second hematology sample will be collected for local assessment of reticulocyte count,*

- If the following pattern of abnormalities is noted:
  - Reticulocyte count  $>$  Central Lab (or if applicable, local lab) upper limit of the reference range (also referred to as ULN) **AND**
  - Haptoglobin  $<$  Central Lab's lower limit of the reference range (also referred to as LLN) **AND**
  - LDH  $>$  ULN **AND**
  - Indirect bilirubin  $>$  ULN (only if the total bilirubin  $>$  ULN)

The patient should be referred to a hematologist. The hematologist should obtain a peripheral blood smear and anti-erythrocyte antibodies (direct and indirect) by Coombs test. Further investigations are at the discretion of the hematologist.

- If the results are normal or the pattern of abnormality is something other than that described above, then the Investigator should exercise his/her medical judgment in the interpretation of the results, necessity for workup of the decrease in hemoglobin or referral to a hematologist

If a second hemoglobin measurement demonstrating a further decrease of  $\geq 1$  g/dL from the last available value is observed, even if the previous work-up was negative, the same investigations can be repeated and a hematology consultation can be requested at the discretion of the Investigator or at the Sponsor's request.

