3.1.4.3 Laboratory safety variables

Clinical laboratory data consists of blood analysis, including hematology, clinical chemistry, and urinalysis. Clinical laboratory values after conversion will be analyzed into standard international units. International units will be used in all listings and tables. Clinical laboratory values converted into conventional (US) units will be also available in the database. Analyses can be provided upon request.

Blood samples for clinical laboratories will be taken as described in the study flow chart in the protocol.

The laboratory parameters will be classified as follows:

- Hematology
 - **Red blood cells and platelets**: hemoglobin, hematocrit, red blood cell count, platelet count;
 - White blood cells: white blood cell count, neutrophils, lymphocytes, monocytes, basophils, eosinophils.

- Clinical chemistry
 - **Metabolism:** fasting plasma glucose, total protein, albumin, creatine phosphokinase (CPK);
 - Electrolytes: sodium, potassium, chloride, calcium, phosphorus, bicarbonate;
 - Renal function: creatinine, eGFR, blood urea nitrogen, uric acid;
 - Liver function: alanine aminotransferase (ALT), aspartate aminotransferase (AST), alkaline phosphatase (ALP), gamma glutamyl transferase (γGT), lactate hydrogenase (LDH), total bilirubin, and in case of total bilirubin values above the normal range, must include direct and indirect bilirubin (used for describing individual cases only);
 - Hepatitis screen: anti-hepatitis-C antibody.

Technical formulas are described in Section 3.5.1.

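### The SAP counts hemolytic anemia only after a confirmed diagnosis, gives no by-arm count of the protocol's laboratory pattern or of unconfirmed cases, and omits reticulocyte count

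*SAP*

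**What the plan says.** **Protocol.** Section 10.4.6.1 deals with a hemoglobin decrease whose reflex tests point to red-cell destruction: "suggesting hemolysis, then report this as an AESI with immediate notification". It does not ask for a confirmed diagnosis at that stage. Section 10.4.7 sets the fall at 1.5 or more "g/dL decrease from pre-randomization baseline value". Section 10.4.7.1 says that at the first post-randomization visit with such a fall "the Central Lab will reflexively measure haptoglobin using specimens already obtained at the same time point". It then defines the pattern: reticulocytes above the upper limit, haptoglobin below the lower limit, LDH above the upper limit and, where total bilirubin is raised, indirect bilirubin above the upper limit. A patient with that pattern goes to a hematologist for a smear and Coombs tests. The routine hematology list in section 9.2.2 reads "red blood cell count, reticulocyte count, hemoglobin, hematocrit, platelets", followed by white cells. Section 11.4.3.2 plans summary statistics for every laboratory variable.

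**SAP.** Section 3.1.4.1 selects the event as "Hemolytic anemia, selected using e-CRF specific tick box on the adverse event page and confirmed final diagnosis provided in the adverse event complementary form". Section 3.1.4.3 lists the red-cell and platelet variables as "hemoglobin, hematocrit, red blood cell count, platelet count". LDH and total bilirubin are kept under liver function, and indirect bilirubin is reserved for individual case descriptions. Section 3.4.5.3 summarizes hemoglobin decreases of at least 15 g/L by treatment group.

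**The concern.** The protocol builds a laboratory route to detecting hemolysis: a trigger, reflex tests on stored specimens, a defined pattern and immediate notification. The SAP counts only the end of that route. A patient who meets the protocol's reporting criterion but never reaches a confirmed final diagnosis falls outside the SAP's AESI count.

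Such patients are foreseeable. Protocol 10.4.7 encourages sites to follow the algorithms but leaves room for investigator judgment, and 10.4.7.1 leaves investigations beyond the smear and Coombs tests to the hematologist. The SAP handles the other laboratory-triggered AESI in the same list, the ALT increase, differently: it is taken directly from laboratory data. No reason is given for the difference.

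At stake is whether the report can show, by arm, how many patients met the criterion the protocol set for this event, and whether the reticulocyte results collected for the purpose are summarized at all.

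**Working it through.** **1. Trigger threshold.** Protocol: 1.5 g/dL. SAP: 15 g/L. Conversion: 1.5 g/dL × 10 dL/L = 15 g/L. The two agree exactly, so the fall that starts the work-up is summarized by arm. What is missing is the outcome of the work-up.

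**2. Each element of the pattern against the SAP.**

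| Element (protocol 10.4.7.1) | Routine list in protocol 9.2.2? | By-arm analysis in the SAP text |
|---|---|---|
| Hemoglobin fall ≥1.5 g/dL | Hemoglobin, yes | Yes, ≥15 g/L (3.4.5.3) |
| Reticulocytes high | Yes | None: absent from 3.1.4.3 |
| Haptoglobin low | No, reflex test only | None found |
| LDH high | Yes | Yes, on its own |
| Indirect bilirubin high, if total bilirubin raised | Total bilirubin, yes | Total only; indirect for case descriptions |
| All elements together | Not applicable | None found |

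Reticulocyte count is collected at randomization, Month 12, yearly after that, and at the final or early end-of-treatment visit. Some sites draw an extra sample for local measurement. The change tables in SAP 2.1 and 2.2 do not record its removal, although they cover major changes only.

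**3. Where an unconfirmed case appears.** There are three possibilities.
- Reported as an adverse event: it enters the all-TEAE tables under its preferred term, because SAP 3.4.5.1 tabulates every TEAE.
- Reported under a term common enough for Tier 2: the term also gets a hazard ratio by arm. The SAP sets the cut-off at the n for which n versus 0 cannot give p below 0.05, but names no test. Assuming a two-sided Fisher exact test and 9,000 to 9,300 patients per arm, p is close to 2 × 0.5^n. For 5 versus 0 this gives p = 0.062, and for 6 versus 0 p = 0.031, so n = 5 and a term needs at least 6 patients overall. With a one-sided test, 4 versus 0 gives 0.062 and 5 versus 0 gives 0.031, so at least 5 are needed.
- Not reported: it is seen only as one of the hemoglobin falls of at least 15 g/L, whatever their cause.

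In none of these is the group counted as a group. Cases may also be spread over several preferred terms, which keeps each term's count low.

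**The case against.** The strongest reply is that a reporting trigger need not be an analysis definition. Protocol 9.2.1 names the event hemolytic anemia, which is a diagnosis, and 10.4.7.1 uses the pattern to start a work-up. Protocol 11.4.3.1 defines AESI tables by preferred term or prespecified grouping, so counting the result of the work-up is coherent and breaches no stated analysis rule. SAP 3.4.5.1 also names hemolytic anemia among events expected to be too rare for useful statistical comparison, where medical judgment should lead. All of this stands. It argues against a formal test, not against a descriptive count beside the confirmed one.

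A reader might infer three stronger things that the documents do not support.
- *Laboratory-suggested hemolysis is never compared by arm and unconfirmed cases vanish.* This is too strong. Hemoglobin falls, LDH and total bilirubin are summarized by arm, and reported cases stay in the TEAE tables, with a hazard ratio if frequent enough.
- *The SAP dropped haptoglobin.* It was never in the protocol's routine list, which treats reflex tests separately. Only reticulocyte count was left out.
- *Bleeding swamps the hemoglobin table in this population.* The documents give no bleeding rate; protocol 8.8.2 merely lists antiplatelet agents among expected treatments. All that can be said is that a hemoglobin fall is not specific to hemolysis.

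**Conclusion.** The point holds as a gap in safety tabulation. The SAP's count is narrower than the protocol's reporting criterion; the combined pattern and the unconfirmed cases have no by-arm count of their own; and reticulocyte count is missing although the protocol lists it and plans to summarize it.

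The size cannot be derived, since no rate of hemolysis or of non-confirmation is given. In direction, the confirmed count can only equal or fall below the protocol-defined count, in both arms. The primary and secondary efficacy conclusions are untouched. This is an inexpensive improvement rather than a flaw in the design.

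The conclusion rests on two assumptions. First, the SAP selection requires both the tick box and the confirmed diagnosis, as its wording reads. Second, the unseen appendices do not fill the gap. SAP Appendix A (abnormality criteria) and protocol Appendix D (hemoglobin decrease) are not in the available text. A criterion on reticulocytes or haptoglobin alone is therefore possible, though it would still not give the combined pattern.

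**What to change.** 1. **SAP 3.1.4.3:** add reticulocyte count to the hematology variables and state how local values are handled, since the summary statistics in 3.4.5.3 use central laboratory results.
2. **SAP 3.1.4.1 and 3.4.5.3:** report descriptively, as n (%) by arm in the safety population during the TEAE period, (a) patients who meet the laboratory pattern in protocol 10.4.7.1 or have the tick box marked, and (b) patients with a confirmed diagnosis.
3. **Supporting information:** give the number of patients per arm with reflex results. Neither these patients nor those with a hemoglobin fall should be the main denominator. Both are post-randomization subsets that treatment could change, so a percentage within them is not a randomized comparison. The number is still useful because protocol 10.4.7.1 requires the reflex test at the first qualifying fall and leaves repeats to discretion.

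The cost is SAP wording and one extra descriptive table from data already collected, with no alpha and no change to patient management. The downside is that a few pattern-positive patients with other explanations will be shown and will need medical comment.
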